#### 8.2.2. Study Ablation Procedure Guidelines

#### 8.2.2.1 Recommended Ablation Parameters and irrigation pump settings

In this study protocol, QMODE+ is to be used as the primary mode for pulmonary vein isolation. Only after the investigator deems that QMODE+ is unable to achieve PVI should the study catheter in QMODE be used to complete the procedure.

#### Table 3. RF and Flow Settings during RF applications

	Target	Temp*	Cut-off Temp		Nominal Irrigation
Power	Range	Maximum allowed	Range	Maximum allowed	Nominal Irrigation Flow rate
25-35 W	40-50ºC	50ºC	50- 55ºC	55ºC	4mL**
36- 50W***	40-50ºC	50ºC	50- 55ºC	55ºC	15mL**
90W†	40-60ºC	60ºC	60- 70ºC	70ºC	8mL**

\* Temperatures displayed on the RF generator do not represent tissue temperature or electrode tissue interface temperature.

\*\*A minimum flow rate of 2mL during mapping is recommended.

- \*\*\* RF applications at 36-50W should not exceed 60 sec.
- + The study recommends using this power setting for PVI as a primary ablation Strategy. RF applications at this power setting are limited up to 4 sec. It is recommended to use lower target temperature setting for the posterior wall RF applications.

Note: The QMODE and QMODE+ parameters, presented in Table A, are user-adjustable, in case the investigator deems appropriate.

### 8.2.2.2 QDOT MICRO™ Contact Force (CF) Settings:

When using the study catheter in both QMODE and QMODE+, operators should Target:

- Target CF: 10g
- CF Range: 5-30g

#### 8.2.2.3 Recommended AF Ablation Procedure Sequence

Subjects will arrive to the electrophysiology laboratory for their ablation procedure and will undergo preparation for the procedure per the hospital's standard protocol (discretion of investigator).

*The AF ablation procedure workflow is recommended to follow the sequence below:* 

- Anesthesia or sedation should be delivered per standard EP lab procedure.
- Placement of diagnostic catheters
- Cardioversion if subject not in sinus rhythm (per investigator discretion)
- CARTO® Respiratory Gating (unless using Jet Ventilation)
- Administration of heparin bolus prior to transseptal puncture or immediately following transseptal puncture
- Transseptal puncture
- Following successful transseptal puncture, an anatomic map can be performed, utilizing Lasso® or PentaRay® (or other at investigator discretion)
  - Note: An anatomical map is not required for triggers outside the left atrium (e.g. SVC/CS etc.)
- Placement of esophageal temperature monitoring device (per investigator discretion)

- Confirmation of target ACT is ≥325 sec (but preferable 350 sec) prior or immediately after transseptal but no later than first ablation into the left atrium and maintain throughout the procedure
- Introduction of the QDOT MICRO™ catheter
  - Use the AUTOTAG feature in CARTO® 3 (Version 6.0 or above) to tag each QMODE+ ablation point after each application
  - At the new location ensure catheter stability before commencing RF application.
  - A pre-ablation flow rate delay of minimal 2 seconds will occur before RF application
  - Ablation modality: RF power application of up to 90W for up to 4 seconds (QMODE+)
  - Move the catheter to a new location (~4mm) if clinically effective ablation is achieved
  - QMODE+ should be used for full PV encirclement. If the investigator deems that QMODE+ is unable to achieve PVI, the study catheter in QMODE should be used to complete the procedure
  - $\circ$   $\,$  Continue RF applications and catheter movement until the circumferential PVI is completed.
  - Precautions:
    - If the temperature increases above the temperature cutoff (default 65°C), RF application will stop immediately (automatically)
    - The decision to interrupt RF power delivery at any time during ablation should be guided by Clinical Investigator judgment and the monitoring of ablation effectiveness parameters commonly used such as EGM reduction and/or impedance changes.
- All subjects will continue PV ablation until PVI is achieved and isolation is confirmed by Lasso® or PentaRay® (or other at investigator discretion).
- After PVI is confirmed, it's recommended to initiate a 20-min waiting period
- Verify the ablation lines with a mapping catheter (Lasso® or PentaRay® or other at investigator discretion)
- Perform additional applications, if required
- Administer adenosine or isoproterenol for each targeted PV to rule out dormant conduction, mandatory unless subject is contraindicated for adenosine
- Perform additional applications (touch-up), if required
- Confirmation of entrance block of all targeted PVs

#### 8.2.2.4 Ablation Procedure Guidelines

#### General Introduction of the Study Catheter

When ablating near adjacent anatomical structures, take precautions to minimize collateral damage to the adjacent structures:

- When ablating near the esophagus (along the posterior wall of the left atrium), take precautions to avoid injuring the esophagus
- Prior to ablation in the region of the right superior PV, precautionary measures are recommended to evaluate proximity to the phrenic nerve, such as pacing maneuvers

#### Ablation outside the PV Ostia

The ablation procedure includes PVI, ablation of non-PV triggers and substrate modification. For RF application outside the PV ostia QMODE+ and QMODE may be used at the discretion of the Investigator.

### 8.2.3. Data Collection During Study Ablation Procedure

Procedural data collection will be done through generator files, CARTO® datafiles, procedural worksheets and subject medical files. Documentation of procedural data will be kept in the subject's CRF, back-up generator files and back-up CARTO® log files for study analysis.

At the completion of the study ablation procedure two back-up copies of the CARTO® 3 and generator log files will be made. One copy should be kept at the site within the investigator site or patient binders, and one fully anonymized copy will be sent to the sponsor, in a timely manner

The Carto and Generator data (electronic raw data) collected during the Study Ablation procedure will be anonymized (or de-identified) prior to its transfer to the Sponsor. Data will be verified during this lifecycle (Data Transfer) to ensure the records are complete and are traceable to subjects within each clinical site. Data will be archived per the applicable policies and procedures as it relates to Data Extract process, Record Retention etc., and will be the source for data analysis. During data transfer, redundant copies will be stored at each critical stage of the transfer to safeguard adequate control over business continuity or disaster recovery of records. A copy of the electronic raw data will also be stored at each clinical site until receipt and storage by the sponsor has been confirmed.

The information collected during the procedure will include, but will not be limited to, the list below.

- RF application-mode per lesion (QMODE+ /QMODE)
- Number of RF applications with QDOT MICRO™ catheter (total/QMODE+/QMODE)
- Duration of RF applications with QDOT MICRO™ catheter (total/QMODE+/QMODE)
- PVI ablation time (time between first RF application and last RF application on a PV before isolation confirmed and circumferential ablation achieved)
- Subject PVI ablation time (time between first RF application and last RF application before all PVI complete)
- Subject total ablation time (time between first RF application and last RF application in a subject)
- Ablation parameters per RF application from the generator files
- Touch-up applications
- Total procedure time (from first femoral puncture to last catheter removal)
- Mapping time
- Fluoroscopy time
- LA catheter dwell time (from ablation catheter LA insertion to ablation catheter removal from the LA)
- ECG data
- Total fluid delivered via ablation catheter and via intravenous line (if captured); fluid output and net fluid input (if captured)
- Strategy used to minimize risk of esophageal injury, if any
- Abnormal esophageal temperature rises (if captured)

### 8.2.4. Pre-Discharge Assessments

Prior to hospital discharge, the following assessments should be performed:

- **Cardiac medication and anticoagulation regimen** (only cardiac related AADs, anticoagulation regimen, etc.)
- **ECG** in case of standard of care
- Adverse events, if any

• Occurrence of AF or other arrhythmias, if any

### 8.3. Post-Ablation Follow-up Schedule and Final Study Visit

The subject will be required to complete follow up visit at 7 days (phone call or clinic visit) post procedure.

Discharged subjects will receive a telephone call or clinic visit at (7D, day -1 or +3) post ablation procedure to assess medication, AF occurrences and Adverse Events.

The subject will be required to complete follow up through 3 months post initial ablation procedure. The follow-up visit is 3 months  $\pm$  14 days (3M, day 76-104) post ablation procedure. Follow-up visit schedule should be based on the date of the index study ablation procedure and will not reset if subject undergoes a repeat AF ablation procedure.

- At the 3 months post ablation procedure visit (in-clinic or telehealth visits) the following assessments should be performed:
  - **Cardiac medication and anticoagulation regimen** (only cardiac related AADs, anticoagulation regimen, etc.)
  - Medical / Hospitalization History
  - **ECG** at the discretion of the investigator
  - Adverse events, if any
  - Assessment of AFL/AT/AF occurrence and repeat ablation
  - End of Study Follow up

### 8.4. Early Termination Visit

Subjects may withdraw from the clinical investigation at any time. The decision for the subject to withdraw informed consent must be made independently of influence by the investigator or site personnel. The subject's decision will be documented in the source and eCRF. The investigator may also choose to withdraw a subject from the study if there are safety concerns. If a subject withdraws from the study, the date and reason for withdrawal will be recorded on the appropriate electronic case report form (eCRF).

All data will be collected (as available) until the subject is withdrawn. If the subject is withdrawn due to an adverse event (AE) or serious adverse event (SAE), the investigator should follow the subject until the AE/SAE has resolved or is considered stable. The local CHU will collect the resolution information of any reported SAEs.

### 8.5. Schedule of Events Table

This table displays the required schedule for subject treatments and evaluations. Subjects should undergo procedure within 60 days of signing informed consent.

#### Table 4. Summary of Subject Assessments

Assessments	Pre- ablation	Procedure	Pre- discharge	7D (D6-10)	M3 (D76-104)
Clinic visit	•	•			• 
Phone Call				• 	
Patient Informed Consent 	•				
Demographics 	•				
Medical/AF history	•			•	•
Cardiac and Anticoagulation Medications	•		•	•	•
Ablation Assessment		•			
ECG			• 	• 	● 
Pregnancy Test	• 				
LA thrombus detection	• 				
Adverse events/Device Deficiency 	•	٠	•	٠	•
AF recurrences			•	•	•

1. May be conducted as a clinic visit (ECG performed if Clinic visit) or a telehealth visit.

2. To be completed within 48 hours prior to ablation procedure

3. In all women of childbearing age and potential. To be completed within one week prior to ablation procedure.

4. Device Deficiency to be collected at ablation and pre-discharge

5. If completed at the investigator's discretion.

# 9. Assessment of Safety

## 9.1. Specific Safety Parameters

### 9.1.1. Definition of Adverse Events (AE)

An AE is any untoward medical occurrence in a subject whether or not related to the medical device under study.

Specifically, an adverse event (AE) is any undesirable experience (sign, symptom, illness, abnormal laboratory value, or other medical event) occurring to a subject during the course of the study, whether or not it is related to the device or procedure. Physical findings (including vital signs) observed at follow-up, or pre-existing physical findings that worsen compared to baseline, are considered adverse events.

Any medical condition that is present at the time that the participant is screened will be considered as baseline and not reported as an AE. Such conditions should be added to background medical history, if not previously reported. However, if the study participant's condition deteriorates at any time during the study, it will be recorded as an AE.

AF recurrence by itself is considered a recurrence of disease (pre-existing condition), and, therefore, does not meet the definition of an AE. Recurrence of pre-existing AFL/ atrial tachycardia (AT) is also considered recurrence of disease and does not meet the definition of an AE.

The following clinical events will not be considered an adverse event for this clinical study:

- A trace / trivial pericardial effusion that is asymptomatic, requires no medical intervention, and does not extend hospitalization will not be considered an adverse event
- AF/AFL/AT recurrence requiring pharmacological or synchronized electrical cardioversion during the hospitalization for the index ablation procedure
- AF/AFL/AT recurrences throughout the duration of the study, as they will be reported as within the effectiveness analysis of early recurrences during the blanking period via arrhythmia monitoring data collection per consensus guidelines.
- However, the development of a new atrial arrhythmia deemed as not an effect of the ablation procedure (in example new onset of left atrial flutter occurring post-ablation) is an AE.
- Re-ablation for AF or preexisting AFL/AT itself is not an AE, however any procedural complication is considered an AE and shall be reported within the applicable timelines

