#### Table 5. Intensity or Severity Definitions

### 9.2.2. Relationship to Study Device

For all collected AEs, the clinician who examines and evaluates the participant will determine the AE's causality based on temporal relationship and his/her clinical judgment. The degree of certainty about causality will be graded using the categories below.

Caused By	Relationship	Definition of Relation
	Causal	The event is associated with the device under study beyond reasonable doubt
	Probable	The relationship with the use of the device under study seems relevant and/or the event cannot reasonably explained by another cause, but additional information may be obtained
Device	Possibly	The relationship with the use of the device under study is weak but cannot be ruled out completely
	Unlikely	The relationship with the use of the device under study seems not relevant and/or the event can be reasonably explained by another cause, but additional information may be obtained
Not Related		Relationship to the device under study can be excluded
Causal		The event is associated with the study procedure beyond reasonable doubt
Chudu	Probable	The relationship with the study procedure seems relevant and/or the event cannot be reasonably explained by another cause, but additional information may be obtained
Study Procedure	Possibly	The relationship with the study procedure is weak but cannot be ruled out completely
	Unlikely	The relationship to the study procedure seems not relevant and/or the event can be reasonably explained by another cause, but additional information may be obtained
	Not Related	Relationship to the procedure can be excluded

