### 9.2.4. Anticipated Adverse Event

An anticipated Adverse Event is an effect which by nature, incidence, severity or outcome has been identified as a possible complication associated with the investigational medical device and/or intervention procedure.

Potential adverse events that are reasonably anticipated to occur during the cardiac electrophysiology procedure are listed in Table 8. These events should be reported via EDC as anticipated AEs.

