#### **Table 8. Comprehensive List of Anticipated AEs**

Anticipated Adverse Events	
Acute Respiratory Distress Syndrome (ARDS)	Air embolism
Allergic reaction	Allergic reaction to Anesthesia (e.g., hair loss)
Anaphylactic shock	Anemia
Anesthesia reaction	Apnea - sedation induced
Arrhythmia: bradycardia	Arrhythmia: pro-arrhythmias
Arrhythmia: tachycardia	Aspiration pneumonia
Asthmatic attack	Atelectasis
Atelectasis	Atrial fibrillation*
Atrio-Esophageal fistula	Atypical left atrial flutter
AV fistula	Bleeding complications
Bleeding requiring transfusion	Cardiac arrest
Cardiac perforation	Cardiac thrombo-embolism
Cerebro-vascular accident (CVA) / stroke	Chest pain/discomfort
Complete heart block, temporary or permanent	Conduction block: ongoing / resolved

Congestive Heart Failure	Coronary artery dissection
Coronary artery occlusion	Coronary artery spasm
Coronary artery Thrombosis	Damage to the vascular system
Death	Deep venous thrombosis
Diaphragmatic paralysis	Dislodgement of permanent pacing leads
Disseminated Intravascular Coagulation	Dyspnoea
Endocarditis	Epistaxis
Esophageal Injury	Exacerbation of pre-existing
	arrhythmia*
Expressive aphasia	Fainting
Fatigue	Gastric reflux
Gastrointestinal diverticulosis	Gastro-intestinal NOS
Heart Failure	Hematoma (local) /ecchymosis
Hemorrhage	Hemothorax
High / increased creatine phosphokinase	Hypotension
(СРК)	
Нурохіа	Increase in frequency or duration of
	episodes of typical atrial flutter
Increased phosphokinase level	Infection, localized
Infection, systemic	Injury to skin, muscle, connective tissu
	due to body position, electrical
	cardioversion, etc.
Laceration	Leakage of air or blood into the lungs
	or other organs due to perforation
Liver toxicity	Mobile strands in Inferior Vena Cava
Myocardial Infarction	Nausea
Neurological disorders (headache)	Neurological disorders (poor
	coordination)
Neurological disorders (tremor)	Obstruction to the vascular system
Palpitations	Perforation to the vascular system
Pericardial effusion without tamponade	Pericardial effusion resulting in
	tamponade
Peripheral embolus	Pericarditis
Peripheral thromboembolism	Peripheral nerve injury
Phrenic nerve damage	Phlebitis
Pneumothorax	Pleural effusion
Pulmonary edema	Pseudoaneurysm
Pulmonary hypertension	Pulmonary embolism
Pulmonary vein dissection	Pulmonary toxicity, like acute
	pulmonary syndrome
Pulmonary vein thrombus	Pulmonary vein Stenosis
Renal failure	Pump failure
Respiratory failure	Respiratory depression

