### 9.4. Reporting Procedures

### 9.4.1. Adverse Event Documentation and Reporting Requirements

Subjects should be encouraged to report AEs spontaneously or in response to general, nondirected questioning (e.g. "How was your health been since last visit?"). Anytime during the study, the subject may volunteer information that resembles an AE.

Each AE must be reported to the sponsor regardless of classification, seriousness, intensity, outcome or causality. The investigator is responsible for ensuring that all AEs observed by the investigator, or reported by the subject, that occur from the time that the subject has signed the informed consent through the end of the study are properly assessed, recorded, and reported as defined and described in the AEs, Adverse Device Effects and Device Deficiencies section of this protocol. All adverse events must be documented by completing subject's medical records (source documents) and appropriate eCRF by the investigator or study coordinator throughout

the study and provided to the Sponsor. All AEs will be monitored until they are adequately resolved or explained.

Anonymized documentation pertaining to the AE (e.g. laboratory tests, consultation reports, postmortem reports, new information relating to a previously reported AE, correspondence with the local EC, etc.) will be provided by the investigator to the sponsor or designee in a timely manner, when requested. Follow-up reports relative to the subject's subsequent course must be submitted to the sponsor or designee until the event has resolved or, in case of permanent impairment, until the condition stabilizes. If the subject is withdrawn from the study because of the AE, the information must be included on the appropriate eCRFs.

The sponsor is responsible for the classification of AEs and ongoing safety evaluation of the study and shall review the investigator's assessment of all AEs. The sponsor will determine and document in writing their seriousness and relationship to the investigational device. In case of disagreement between the sponsor and the principal investigator(s), the sponsor shall communicate both opinions to the concerned parties.

Biosense Webster will ensure that investigators are instructed to return devices suspected of causing an AE or SAE (i.e., definitely device-related or possibly device-related) in accordance with relevant regulations and current company procedures.

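### Section 9.1.1 refers arrhythmia recurrences to an effectiveness analysis that Section 14 does not contain, and its new-arrhythmia bullet implies that adverse event status depends on relatedness to the ablation

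*Combined protocol and SAP*

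**What the plan says.** **Recurrences.** Section 9.1.1 lists events that are not adverse events. AF, AFL and AT recurrences during the study are on the list because "they will be reported as within the effectiveness analysis of early recurrences during the blanking period via arrhythmia monitoring data collection per consensus guidelines". The same section, and the footnote to Table 8, also give an independent ground: recurrence is return of a pre-existing disease. Re-ablation for AF or pre-existing AFL/AT is excluded as well, although its complications remain adverse events.

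**New arrhythmias.** A further bullet in that list, opening with a contrast word, says that "the development of a new atrial arrhythmia deemed as not an effect of the ablation procedure" is an adverse event. Its example is new left atrial flutter after the ablation. The general definition earlier in 9.1.1 covers any undesirable experience "whether or not it is related to the device or procedure". Section 9.4.1 adds: "Each AE must be reported to the sponsor regardless of classification, seriousness, intensity, outcome or causality". Table 8 lists "Atypical left atrial flutter" and pro-arrhythmias among the anticipated events, and 9.2.4 says of the Table 8 events: "These events should be reported via EDC as anticipated AEs". The asterisk that exempts a Table 8 entry is attached only to atrial fibrillation and to exacerbation of a pre-existing arrhythmia.

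**The concern.** There are two separate problems in one list.

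First, the protocol says recurrences will be reported and names the place, but that place does not exist. Recurrences are barred from the adverse event tables and have no effectiveness table either, so outcomes that sites are asked to collect up to month 3 have no planned summary. Repeat ablation is in the same position.

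Second, the qualifier in the new-arrhythmia bullet has no function unless it limits which new arrhythmias are adverse events. Read that way, it removes the ones most attributable to the procedure. Section 1.2.1 names acute safety as a main objective. Sites that read the bullet differently would record the same event differently, and the incidence of adverse events and of procedure-related adverse events would then partly reflect the reading.

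**Working it through.** This is mainly a comparison of texts. The plan has no hypothesis, alpha or power figure to reproduce.

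**Part 1: does the promised recurrence analysis exist?** The sentence in 9.1.1 has three elements.

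- *The analysis.* Section 14 states that it is the SAP and that it describes all analyses. Section 14.4.4 covers acute procedural success. Section 14.4.5 covers procedure times, isolation by mode, touch-up, RF counts and locations, generator logs, and temperature, power, force and impedance. Neither mentions recurrence or repeat ablation. Section 3.2.2 leaves its list of additional data open but does not name recurrence.
- *The blanking period.* This document does not define it; it is left to consensus guidelines.
- *The arrhythmia monitoring.* No systematic rhythm monitoring is scheduled. The day-7 and month-3 contacts may be remote. ECG is discretionary under 8.3 (month 3) and footnote 5 of Tables 1 and 4, in tension with footnote 1, which has it performed at clinic visits.

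What is collected: AF or other arrhythmias before discharge (8.2.4), AF at day 7 (8.3), and AFL/AT/AF and repeat ablation at month 3 (8.3). That is 3 time points, against 0 planned summaries.

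Interval between the two post-discharge contacts, from the windows day 6–10 and day 76–104:

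- shortest: 76 − 10 = 66 days
- longest: 104 − 6 = 98 days

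**Part 2: does adverse event status depend on relatedness?**

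| Source | Does relatedness decide whether it is an adverse event? |
|---|---|
| 9.1.1, general definition | No |
| 9.1.1, new-arrhythmia bullet | By implication, yes |
| 9.2.4 and Table 8 | No; new flutter and pro-arrhythmia are listed without exemption |
| 9.4.1 | No, but it applies only once an event is treated as an adverse event |

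The bullet sets a yes/no test, while 9.2.2 grades relatedness in five steps and the two are not linked. Section 14.4.6 counts four of the five grades (unlikely, possible, probable, causal) as procedure-related. So if a site takes the bullet's test to mean the grade *not related*, every new atrial arrhythmia it records falls outside the procedure-related table. If it also admits *unlikely*, those events enter the table while the possible, probable and causal ones stay out. Neither result can be intended.

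Section 14.4.6 counts only events on the adverse event CRF page, so an event left off that page is not recovered by the analysis.

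**Size of one omission.** Under 14.4.1, adverse event percentages use the number of subjects in the analysis population. Taking the planned range of 30 to 50 as that denominator:

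- 1/30 = 3.3 percentage points
- 1/50 = 2.0 percentage points

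This is the change in the by-subject percentage for the term concerned. The any-adverse-event percentage moves by the same amount only if that subject has no other adverse event.

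**The case against.** On recurrences: recurrence is not an objective, the primary endpoint or a named additional endpoint, so no planned endpoint lacks an analysis. The defect is one clause in a definition, and the exclusion from adverse events does not need that clause. Deleting it would restore consistency. Repeat ablation goes beyond what the clause promises. The 66 to 98 days between contacts say nothing about a missing analysis, and subjects are asked about events since the last visit.

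Most of this stands. Deletion is a sufficient repair, the exclusion is sound on its other ground, and the interval describes the data without itself being a defect. Two points do not stand. An open list of data to be collected does not supply a definition, a summary or an analysis set. And the enquiry about events since the last visit (9.3) concerns adverse events, which recurrences are not.

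On new arrhythmias: no sentence says that an ablation-related one is not an adverse event. No exclusion in 9.1.1 names new arrhythmias, so the general definition would apply by default. Section 9.2.4 with Table 8 directly tells sites to report atypical left atrial flutter, and the bullet's own example points to recording it. Clumsy drafting is a fair reading. The 3.3 and 2.0 points are simply 1/n and would hold for any miscounted event.

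This makes omission a risk and not a certainty, and it shows that no loss has been demonstrated. It does not remove the contradiction: a site would have to set the bullet's qualifier aside in order to follow the other passages.

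**Conclusion.** Both parts hold. The reference in 9.1.1 has no counterpart in Section 14: 3 collection points, 0 summaries. The new-arrhythmia bullet conflicts, by clear implication, with the general definition in its own section and with Table 8.

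The consequence is limited to reporting. The study is descriptive and the primary endpoint, acute procedural success, is untouched. The documents give no rate of recurrence or of new arrhythmia and none is assumed here, so the expected effect on the tables cannot be stated. What can be stated is the effect per omitted subject: 3.3 points at 30 subjects and 2.0 at 50, assuming the safety set lies in the planned range. Confidence is high that the passages disagree. Whether any site would actually omit an event is uncertain. The changes should be made, but they are not critical.

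**What to change.** 1. Make 9.1.1 and Section 14 agree. Preferably, add to 14.4.5 one descriptive by-subject summary and a listing of the recurrence and repeat-ablation data already collected. State the analysis set (the 14.4.5 default is the effectiveness analysis set) and label the result as not based on systematic rhythm monitoring. If the blanking-period wording is kept, define the period in the document. The alternative is to delete the reference from 9.1.1 and let the exclusion rest on recurrence of disease.
2. Reconcile the new-arrhythmia bullet with the general definition, 9.4.1 and Table 8, so that adverse event status does not depend on relatedness. Section 9.2.2 already grades relatedness separately.

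The cost is two wording corrections in 9.1.1 and, under the preferred option, one table and one listing. No new visit, test or data item is needed. Adverse event counts may rise slightly.
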